5.1. Dose Justification

The present study (324-ETD-303) is a long-term, open-label study to evaluate the safety and tolerability of SAGE-324 in participants with ET. The dose selected for the study is the highest dose that is included in the dose-ranging study 324-ETD-202. Once the dose-ranging study is completed and a dose or doses are selected for inclusion in pivotal studies, this protocol will be amended to employ the highest of the doses included in the pivotal studies. This is in line with the ICH E1A guideline, requiring exposure at the dosage level(s) intended for clinical use.

In order to mitigate the adverse event (AE) of somnolence that was observed in study 324-ETD-201, nighttime dosing will be employed as well as an up-titration to the 60-mg dose (Section 7.3). Up-titration is a standard practice that is designed to allow participants to accommodate to the AE as plasma concentrations rise more slowly than they would if the target dose was administered from the start. Participants will be allowed to down-titrate at any time if intolerable AEs occur.

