7.3. Treatment Assignment

SAGE-324 will be self-administered orally once daily in the evening before bed, with a snack if bedtime is not within 2 hours of the evening meal.

Participants will self-administer 15 mg SAGE-324 on Day 1 to Day 14, 30 mg on Day 15 to Day 28, 45 mg on Day 29 to Day 42, and then 60 mg daily starting on Day 43.

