7.4. Dose Adjustment Criteria

If a participant experiences AEs at any time during the Treatment Period that are considered by the investigator to be related to the IP and not tolerable, the investigator may reduce the dose of

IP in 15 mg decrements, including during the initial dose escalation period. Administration of IP will be interrupted for 3 to 8 days before the initiation of the reduced dose.

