8. STATISTICAL ANALYSIS

8.1. General Considerations

All participant data, including those that are derived, that support the tables and figures will be presented in the participant data listings. Some data may be presented only in participant data listings, some may be presented with a corresponding table or figure; these will be indicated in relevant sections below.

For all safety [REDACTED] analyses where applicable, baseline is defined as the last non-missing measurement prior to the first dose of IP. For scores that are made up of item scores, all item scores must come from the same visit to be considered as baseline for the overall score.

Continuous endpoints will be summarized with n, mean, standard deviation (SD), median, first and third quartiles (Q1, Q3), minimum (min), and maximum (max). The minimum and maximum will be reported with the same number of decimal places as the source (raw) data. Mean and median will be reported to 1 decimal place more than the source (raw) data and standard deviation will be reported to 2 decimal places more than the source (raw) data. Any values that require transformation to standard units (metric or SI) will be converted with the appropriate corresponding precision. In addition, change from baseline values will be calculated at each time point and summarized descriptively.

Categorical endpoints (eg, incidence of an adverse event) will be summarized using counts and percentages. Percentages will be presented to 1 decimal place unless otherwise specified.

Participants will be summarized according to treatment received. “By-visit” summaries are based on the last dose received before the specific evaluation. Adverse events summaries are based on the last dose received before the start of the AE. Note that it is possible for a participant to be counted under more than one dose in summaries. Since baseline is by definition before the first dose of IP, baseline values in listing will have no dose designation, and in summaries it will be presented under “Sage-324 Overall”. For displays for which no such date applies, e.g. demographics, disease history, etc., the presentation will not be by dose group, but will be by aggregate SAGE-324 group.

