8.4. Safety Analysis

Safety and tolerability of SAGE-324 will be assessed based on TEAEs, changes from baseline in clinical laboratory evaluations, 12-lead ECGs, and vital signs, C-SSRS, PWC-20, and ESS. Safety data will be listed by participant.

For safety summary tables, the safety endpoints evaluated at scheduled visits are taken as done and nominal visit will be summarized as scheduled visits. For multiple values from the specific visit window, the choice of the visit record will be following the same rule as described in [Section 8.3.2](#).

All safety summaries will be prepared by dose level and overall for the Safety Set. See [Table 4](#) for details on how safety endpoints will be presented.

Table 4: Presentation of Safety Endpoints

Safety Evaluation	Incidence	Raw Value	Change from Baseline	Abnormality	Derived PCS values
TEAEs	X	*			
Vital Signs		X, *	X		X, *
12-lead ECG		X, *	X	X, *	X, * (QTcF only)
Safety Labs (Chemistry, Hematology, Urinalysis)		X, *	X	X, *	X, *
ESS	X	*	X		
PWC-20	X	*			
C-SSRS	X	*	X		

X = Safety Assessment will be summarized in tables
 * = Safety Assessment will be presented in individual participant data listings
 Note: PCS = Potentially Clinically Significant.

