8.4.8. Epworth Sleepiness Scale (ESS)

The ESS is a quick, 8-item, self-administered questionnaire where participants rate, on a 4-point scale of 0 (no chance of dozing) to 3 (high chance of dozing), their usual chances of dozing off or falling asleep while engaged in 8 different activities. The total ESS score estimates the participant's average sleep propensity, across a range of activities in their daily lives ([Johns 2002](#)).

All by-visit ESS summary tables will present results using the Safety Set – overall, and also by dose last received immediately prior to the evaluation. Descriptive statistics for each of the 8 individual items (continuous and by categorical response) at each scheduled visit, the total ESS score at each scheduled visit, and change from baseline in the total ESS score at each postbaseline visits will be presented. The number and percentage of participants with a total ESS score of 0, no chance of dozing off, will also be presented at each visit.

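### From the Day 50 visit, by-visit safety columns for 15, 30 and 45 mg can hold only participants reduced for intolerable AEs, so reading across dose columns partly compares intolerant with tolerant participants

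*SAP*

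**What the plan says.** SAP 8.1 assigns results to dose columns by current dose: by-visit "summaries are based on the last dose received before the specific evaluation". SAP 8.4 makes this general: "All safety summaries will be prepared by dose level and overall for the Safety Set". The laboratory, ECG, vital signs and C-SSRS sections repeat the rule. SAP 8.4.8 does so for sleepiness, with tables "overall, and also by dose last received immediately prior to the evaluation".

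Dose is not randomised. Protocol 7.3 puts everyone on the same steps, ending with "45 mg on Day 29 to Day 42, and then 60 mg daily starting on Day 43". Protocol 7.4 allows a step down when an AE is "considered by the investigator to be related to the IP and not tolerable, the investigator may reduce the dose of" the product. Protocol 5.1 agrees: "Participants will be allowed to down-titrate at any time if intolerable AEs occur". Neither document gives another planned reason for a lower dose.

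The SAP's only note on reading the dose columns is that one person can appear in several of them (8.1). It does not separate titration records from records after a reduction, and it does not caution against comparing columns at later visits.

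**The concern.** A dose label means different things at different visits. Up to the Day 43 visit, the column for the scheduled step holds nearly the whole cohort. Once the schedule has brought everyone to 60 mg, a lower-dose column is reached only by failing to tolerate a dose. Column membership is then a consequence of tolerability, and the tables in question describe tolerability.

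ESS is the most exposed measure. Protocol 5.2 names somnolence as the AE most commonly reported in previous studies, so it is a plausible reason for reduction, and the ESS table would then sort people by something close to its own outcome. A reader who takes a later row as dose response could conclude that sleepiness or orthostatic change is no worse, or even milder, at 60 mg than below it, when the row shows who was reduced.

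**Working it through.** The plan states no figure for this point, so there is none to reproduce. Two checks were made.

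**1. Who can be in each column.** Inputs: the dosing days in Protocol 7.3, evening dosing (7.1), and the visit days and windows in Protocol Tables 2 to 4. With evening dosing, the last dose before a visit on Day d is the dose of Day d − 1.

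| Visit | Last scheduled dose | Across the ±2-day window |
|---|---|---|
| Day 36 | 45 mg | 45 mg |
| Day 43 | 45 mg | 45 or 60 mg |
| Day 50 | 60 mg | 60 mg |
| Day 57 | 60 mg | 60 mg |

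Day 50 is thus the first visit at which every unreduced participant on schedule is on 60 mg. Scheduled on-treatment visits from there to Month 60: 2 (Days 50 and 57) + 5 (Weeks 10, 12, 16, 20 and 24) + 18 (Months 9 to 60, every 3 months) = 25. ESS and vital signs are scheduled at all of them, ECG and laboratory tests at a subset. Reductions are also allowed during escalation, so some selection can begin before Day 50.

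Three qualifications apply. EOT, EOS and last-value rows are not among the 25, because they also hold people who stopped during titration. A participant seen during the 3-to-8-day interruption still has the higher dose as last dose, so 60 mg is not purely tolerant. SAP 8.2.6 foresees unscheduled increases, although the protocol gives no re-escalation rule.

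**2. What selection alone can do.** Assume no dose effect. The most susceptible share p of participants is reduced, and the later outcome correlates ρ with susceptibility. With z the upper-p normal cut-point and φ the normal density, the expected gap (reduced minus 60 mg) in SD units is

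gap = ρ × φ(z) / [p(1 − p)].

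For p = 0.20: z = 0.842, φ(z) = 0.280, and 0.280 / 0.16 = 1.75. With ρ = 0.3 the gap is 0.52 SD; with ρ = 0.5 it is 0.87 SD; with ρ = 0 it is 0.

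A simulation of 750 participants (the planned number, 1,000 runs) agrees. ESS points assume an SD of 4. The flag columns assume a true 10% rate at every dose and show reduced versus 60 mg.

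| p reduced | Gap in SD, ρ = 0.3 / 0.5 | ESS points, ρ = 0.3 / 0.5 | Flag rate, ρ = 0.3 | Flag rate, ρ = 0.5 |
|---|---|---|---|---|
| 10% | 0.58 / 0.97 | 2.3 / 3.9 | 21.6% vs 8.8% | 32.2% vs 7.5% |
| 20% | 0.52 / 0.87 | 2.1 / 3.5 | 18.6% vs 7.9% | 25.7% vs 6.1% |
| 30% | 0.50 / 0.83 | 2.0 / 3.3 | 16.6% vs 7.1% | 21.9% vs 4.9% |
| 40% | 0.48 / 0.80 | 1.9 / 3.2 | 15.3% vs 6.5% | 18.9% vs 4.0% |

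Here p, ρ, the SD and the 10% rate are assumptions; the documents give none of them. If reduction truly lowers the outcome by δ SD, the gap becomes the tabulated value minus δ. At p = 20% and ρ = 0.3, δ = 0.52 removes it and a larger δ reverses it.

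**The case against.** The case against is substantial, and much of it stands.

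- **No dose comparison is planned.** The primary endpoint is TEAE incidence, and most secondary endpoints are changes from baseline. There is no dose test, and Protocol 5.1 refers to a separate dose-ranging study. A reader might infer that the dose columns are the only comparison in this single-arm study. They are not: change from baseline and an Overall column are available, and grouping by last dose does not touch Overall.
- **The main tolerability tables work differently.** A reader might infer that the plan as a whole favours 60 mg. SAP 8.4.1 charges a TEAE to the dose taken just before onset, so an event at 60 mg that leads to a reduction counts against 60 mg.
- **Visits are shown separately.** A reader might think the ESS tables pool titration and reduced records. They are by visit only, so the two sit in different rows. Pooling occurs in the any-time PCS tables, where titration records from nearly everyone dilute the selected group, and where results are assigned to the dose when the criterion was met.
- **Not every measure need be affected.** Nothing in the documents shows that people reduced for somnolence, say, would differ in laboratory values.
- **Related facts are reported.** The SAP tabulates TEAEs leading to reduction and interruption, discontinuation by dose level, and exposure by dose at discontinuation.

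These points limit the harm to reading across dose columns in by-visit tables after titration. They do not make those columns comparable groups, and the related tables do not tell the reader that a later 45 mg row is AE-selected.

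**Conclusion.** The concern holds for post-titration by-visit tables (ESS, vital signs, laboratory tests, ECG). At the 25 scheduled on-treatment visits from Day 50, for participants following the protocol schedule, the 15, 30 and 45 mg columns are selected by intolerance, and the SAP neither separates nor flags this.

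Size and direction cannot be determined from the documents. The calculations show that selection alone could produce roughly half to one SD under moderate persistence of susceptibility; they do not predict the result. It would also be too strong to attach one number to the bias. For example, assuming tolerant participants at +1 and intolerant at +4 on ESS change gives a 3-point gap only because 4 − 1 = 3. Nor do the documents support saying that lower doses will look worse.

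This is a worthwhile, inexpensive improvement to descriptive tables. It does not affect the primary endpoint, the Overall summaries or the assignment of TEAEs to dose.

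**What to change.** In SAP 8.1 and 8.4, derive one flag from the unscheduled-reduction dates already needed for planned exposure in SAP 8.2.6. Then:

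1. For scheduled on-treatment visits from Day 50, present by-visit summaries as 60 mg never reduced, after dose reduction, and Overall. Pool the reduced doses where cells are small and keep the current dose in the listings.
2. In any-time PCS tables, separate scheduled-titration records from after-reduction records.
3. State how records during an interruption, and after an unscheduled increase, are classified.
4. Footnote that after-reduction columns are AE-selected and are not dose response.

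The cost is SAP wording, one derived variable, an additional column and some small cells. No data collection or dosing rule changes. If the database is already locked, SAP Section 2 provides for documenting the change in the clinical study report. If even the extra column is unwelcome, the footnote alone addresses the main risk of misreading, but it does not show the two groups apart.

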12.2. Adverse and Serious Adverse Events

12.2.1. Adverse Event Definition

An AE is any untoward medical occurrence in a participant or clinical investigation participant administered a pharmaceutical product and that does not necessarily have a causal relationship with this treatment. An AE can therefore be any unfavorable and unintended sign (including an abnormal laboratory finding), symptom or disease temporally associated with the use of a medicinal (investigational) product whether or not related to the medicinal (investigational) product. In clinical studies, an AE can include an undesirable medical condition occurring at any time, including baseline or washout periods, even if no study treatment has been administered.

A TEAE is defined as an AE with onset after the start of IP, or any worsening of a pre-existing medical condition/AE with onset after the start of IP and throughout the study. The term IP includes any Sage IP, a comparator, or a placebo administered in a clinical study.

Laboratory abnormalities and changes from baseline in vital signs, and ECGs are considered AEs if they result in discontinuation or interruption of study treatment, require therapeutic medical intervention, meet protocol specific criteria (if applicable) or if the investigator considers them to be clinically significant. Any abnormalities that meet the criteria for an SAE should be reported in an expedited manner. Laboratory abnormalities and changes from baseline in vital signs and ECGs that are clearly attributable to another AE do not require discrete reporting (eg, electrolyte disturbances in the context of dehydration, chemistry and hematologic disturbances in the context of sepsis).

All AEs that occur after any participant has signed the informed consent and throughout the duration of the study, whether or not they are related to the study, must be reported to Sage Therapeutics.

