13.7.1. Adverse Events

AEs will be coded using Medical Dictionary for Regulatory Activities (MedDRA) Version 23.1 or higher. A TEAE is defined as an AE with onset after the first dose of IP. The analysis of AEs will be based on the concept of TEAEs. The incidence of TEAEs will be summarized by System Organ Class and Preferred Term. In addition, summaries will be provided by intensity (mild, moderate, severe) and by causality (related, not related) to IP.

Any TEAEs leading to discontinuation of treatment or withdrawal from the study and any treatment-emergent SAEs will be summarized.

All AEs and SAEs (including those with onset or worsening before the start of IP) through the end of the study will be listed.

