8.4.1. Adverse Events

Adverse events will be coded using MedDRA Version 25 or higher. In the event of a missing/incomplete start or stop date associated with an adverse event, only the treatment-emergence will be imputed using the algorithm described in [Appendix B](#). Dates will not be imputed.

A TEAE is defined as an AE with onset at or after the first dose of IP (SAGE-324). Summary tables of AEs will include TEAEs only and will summarize data using the Safety Set participants overall and by dose level taken immediately prior to the AE onset.

An overall adverse event summary table will be presented for TEAEs and will include the number and percent of participants experiencing at least one:

- TEAE
- Maximum severity of TEAE (mild TEAE, moderate TEAE, severe TEAE)

- TEAE leading to dose interruption
- TEAE leading to dose reduction
- TEAE related to IP
- TEAE leading to IP discontinuation
- TEAE leading to study discontinuation
- Serious TEAE
- Serious TEAE related to IP
- Serious TEAE leading to IP discontinuation
- Serious TEAE leading to study discontinuation
- TEAE resulting in death

The incidence of TEAEs will be summarized by System Organ Class (SOC) and Preferred Term (PT). In addition, summaries will be provided by maximum severity (mild < moderate < severe) and by maximum relationship (related > not related) to IP. Any TEAEs leading to IP discontinuation, any TEAE leading to study discontinuation, and any treatment-emergent SAEs will also be summarized, sorted by descending frequency in SOC and PT.

Participants will be counted only once within each SOC and PT at the maximum severity in the following order: severe, moderate, and mild. Participants will be counted only once within each SOC and PT at the strongest relationship to IP in the following order: related, not related to IP. An AE with missing severity will be considered as 'severe', and with missing relationship to IP will be considered as 'related' for the purposes of summarizing these data.

The incidence of TEAEs and treatment-emergent SAEs will also be presented in order of decreasing frequency by PT.

All AEs (including those with onset before the start of IP) through the end of the study will be listed. In addition, separate listings containing individual participant AE data for all deaths, SAEs, AEs leading to IP discontinuation, and AEs leading to study discontinuation will be provided.

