8.4.3. Electrocardiogram

All by-visit ECG summary tables will present results for Safety Set participants overall, and also by dose level received prior to the evaluation. For summarization of incidence any time post-baseline, participant data will be summarized according to the last dose received when a particular criterion was met (thus, a participant may contribute data under more than one dose if a criterion was met post-baseline while taking different doses). Last value on treatment and last value on study will be summarized under the dose level last received.

The average of any multiple values collected at one visit will be used for summarization of continuous variables, including baseline ECG values. For each ECG measurement (heart rate and PR, QRS, QT, and QTcF intervals), the observed value at each scheduled visit and change from baseline at each scheduled visit will be provided. This summary will also include last values on treatment and on study. Last value on treatment is defined as the last post-baseline value between first dose of IP (exclusive) and up to last dose of IP + 1 day (inclusive). Last value on study is defined as the last post-baseline value after the first dose of IP.

In addition, the number and percentage of participants with PCS and potentially clinically significant change (PCSC) values will be summarized by scheduled timepoint and for any time post-baseline, including last value on treatment and last value on study. Individual values of QTcF will be used for PCS determination rather than the average of multiple values collected at one visit. Potentially clinically significant values will be identified for ECG parameters as outlined in [Table 9](#).

A shift table of overall ECG interpretation from baseline to scheduled post-baseline visits will be presented for the following categories: 'Normal', 'Abnormal, Not Clinically Significant', and 'Abnormal, Clinically Significant'. The shift table will be presented by visit – overall and by dose level.

Clinically significant abnormal findings will be reported as adverse events. The average of any multiple values collected at one visit of each parameter will be included in the data listing.

Table 9: Potentially Clinically Significant Values for QTcF

Units	Criteria for PCS Values (Observed Values)		Criteria for PCSC Values (Change from Baseline)	
	High	Low	Increase	Decrease

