8.4.7. Physician Withdrawal Checklist (PWC-20)

The PWC-20 is a shorter version of the Penn Physician Withdrawal Checklist based on the 20 items that provided the best differentiation from placebo in previous trials. The PWC-20

is made up of a list of 20 symptoms (eg, loss of appetite, nausea-vomiting, diarrhea, anxiety-nervousness, irritability) that are rated on a scale of 0 (not present) to 3 (severe) ([Rickels 2008](#)). The PWC-20 will be used to monitor for the presence of potential withdrawal syndrome following discontinuation of SAGE-324.

Summarization of PWC-20 data will be presented using the Safety Set – overall and by dose last received immediately prior to the evaluation. Descriptive statistics for the total PWC-20 score will be presented at End of Treatment (defined as the first available assessment after the last dose of study within 1 day of last dose) and End of Study. The change from End of Treatment to End of Study in PWC-20 total score will be provided. The number and percentage of participants with each PWC-20 item and reporting severe on a PWC-20 item will be presented at each visit. Descriptive statistics for the number of PWC-20 items and the number of severe PWC-20 items experienced at each visit will also be presented.

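### TEAE tables put events that start after the last dose, or during a dose interruption, under the last dose received and never show them separately

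*SAP*

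**What the plan says.** The primary endpoint is the incidence of TEAEs (SAP 4.1). Three places define a TEAE:

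- SAP 8.4.1: "A TEAE is defined as an AE with onset at or after the first dose of IP (SAGE-324").
- Protocol 13.7.1: "A TEAE is defined as an AE with onset after the first dose of IP".
- Protocol 12.2.1 adds "any worsening of a pre-existing medical condition/AE with onset after the start of IP and throughout the study".

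Protocol 12.2.1 has AEs reported from consent throughout the study. For a participant who stops treatment, the last planned visit is End of Study (EOS), 14 (±3) days after the last dose (Protocol 7.1, SAP 5.1).

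For dose attribution, SAP 8.1 says "Adverse events summaries are based on the last dose received before the start of the AE". SAP 8.4.1 says that AE tables are presented "overall and by dose level taken immediately prior to the AE onset".

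For dose reductions, Protocol 7.4 says "Administration of IP will be interrupted for 3 to 8 days before the initiation of the reduced dose".

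Two other SAP sections treat the time after dosing separately. SAP 8.4.3 defines a last ECG value on treatment, counted "up to last dose of IP + 1 day (inclusive"), and a last value on study. SAP 8.4.7 uses the PWC-20 to "monitor for the presence of potential withdrawal syndrome following discontinuation of SAGE-324".

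**The concern.** The study raises two safety questions: how well SAGE-324 is tolerated while it is taken, and what happens when it is stopped. Under the rules above, an AE that starts ten days after the last 60 mg dose is tabulated as a 60 mg TEAE. An AE that starts on the fourth day of an interruption from 45 mg is tabulated as a 45 mg TEAE. Neither can be told apart in the tables from an event that started while tablets were being taken.

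Two things are at stake. First, a low-dose column can contain a sizeable share of events from undosed days, because each titration step lasts only 14 days. Interruptions follow related, intolerable AEs, so those undosed days come from participants who tolerated the drug poorly, and they are credited to the higher dose. Second, a cluster of new AEs after discontinuation would be spread across the dose columns, and no summary table would show it as a cluster.

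**Working it through.** The plan states no figure on this point, and the sample size of about 750 rests on exposure rather than on an event rate. The check is therefore a reading of the rules, followed by day counts.

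**Reading the rules.** All three TEAE definitions fix only the start. The window closes when AE collection ends, at EOS. The attribution rule offers dose levels and an overall column, with no category for follow-up or interruption. SAP 8.2.6 scores a skipped day as 0 mg, but only for total exposure. The AE rule looks back to a dose received, so no 0 mg column results. Appendix C lists TEAE Tables 14.3.1.1 to 14.3.1.9, and none is split by onset during or after dosing. The SAP 8.4.1 count of TEAEs leading to dose interruption covers events that caused an interruption, not events that began in one.

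**Inputs.** Follow-up is 14 days, 11 to 17 with the visit window (SAP 5.1). An interruption lasts 3 to 8 days (Protocol 7.4). Titration is 14 days each at 15, 30 and 45 mg, then 60 mg from Day 43 (Protocol 7.3).

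**Undosed share of the AE window** = undosed days / (dosing days + undosed days).

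| Dosing days before stopping | 11 days' follow-up | 14 days | 17 days |
|---|---|---|---|
| 14 | 11/25 = 44% | 14/28 = 50% | 17/31 = 55% |
| 20 | 11/31 = 35% | 14/34 = 41% | 17/37 = 46% |
| 42 | 11/53 = 21% | 14/56 = 25% | 17/59 = 29% |
| 365 | 11/376 = 2.9% | 14/379 = 3.7% | 17/382 = 4.5% |
| 1826 (5 years) | 11/1837 = 0.6% | 14/1840 = 0.8% | 17/1843 = 0.9% |

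**One dose column.** A participant who stops on Day 20 has taken 30 mg for 6 days (Days 15 to 20), and all follow-up is credited to 30 mg. The undosed share of that participant's 30 mg time is 14/(6+14) = 70%, with a range of 11/17 = 65% to 17/23 = 74%.

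**Interruption.** After one 14-day step, 3 to 8 undosed days make up 3/17 = 18% to 8/22 = 36% of the time credited to that dose.

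**From time to incidence (illustration only).** The documents give no AE rate. Assume a constant rate r per patient-year, the same on dosed and undosed days, so that incidence = 1 − exp(−r × days/365.25). The participant stops after one 14-day step.

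| Assumed r | 14 dosing days only | Plus 14 follow-up days | Plus a 3 to 8 day interruption instead |
|---|---|---|---|
| 0.5 | 1.9% | 3.8% | 2.3 to 3.0% |
| 1 | 3.8% | 7.4% | 4.5 to 5.8% |
| 2 | 7.4% | 14.2% | 8.9 to 11.3% |
| 4 | 14.2% | 26.4% | 17.0 to 21.4% |

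Under that assumption, follow-up roughly doubles the incidence credited to the step for such a participant. At r = 1 and one year of dosing, the same 14 days move it only from 63.2% to 64.6%.

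**The case against.** The case for leaving the plan alone has real force.

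- **The window does end.** A reader might infer that TEAEs are counted without limit. Protocol 12.2.1 ties them to the study, and EOS falls about two weeks after the last dose. What is missing is a limit tied to exposure.
- **Undosed is not drug-free.** It is tempting to call the follow-up and interruption days off drug and to read the shares as misattributed time. The documents give no half-life (Protocol 12.3 refers to five terminal half-lives without a value), so residual exposure cannot be judged. Nor can a calendar cut sort events caused by the drug from events caused by stopping it. Counting some post-dose days under the last dose is a cautious choice.
- **The ECG section is not a clean contrast.** SAP 8.4.3 also summarises the last value on study under the dose last received. Laboratory tests, vital signs, C-SSRS and PWC-20 follow similar last-dose rules. The AE rule is consistent with the rest of the SAP.
- **Both questions are partly addressed.** TEAEs leading to interruption, reduction and IP discontinuation are counted, and an event that led to stopping will ordinarily have begun during dosing. The PWC-20 is a secondary endpoint with item-level summaries. AE and dosing listings allow individual events to be traced.
- **Early stops are selected examples.** No discontinuation pattern is given, and a share of time is not a share of events.

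All of this limits the point without removing it. The PWC-20 covers 20 fixed symptoms at two visits, and SAP 8.4.7 restricts its End of Treatment value to within 1 day of the last dose, although the visit is scheduled at 3 (±3) days. Listings are not summaries. No planned table shows the incidence of AEs that begin after the last dose.

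**Conclusion.** The point holds as a gap in presentation. TEAEs are counted to EOS and placed under the last dose received, and no listed table separates onset during dosing from onset afterwards or in an interruption.

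The undosed share of the window is 50% (44 to 55%) for a participant who stops after 14 days and 41% (35 to 46%) after 20 days. It falls to 3.7% at one year. The consequence is therefore greatest for the 15, 30 and 45 mg columns and for the visibility of AEs after discontinuation, and small for long-term 60 mg exposure. These shares rest only on the documents' day counts. The incidence illustration also rests on an assumed constant rate.

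A reader might go further and conclude that the primary endpoint is distorted. The documents do not support that: the overall TEAE incidence does not depend on dose attribution, and counting events through follow-up is what Protocol 12.2.1 specifies. The analysis is single-arm and descriptive, so no test or error rate is affected.

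**What to change.** Keep the overall TEAE definition and the existing by-dose tables. In SAP 8.4.1 and Appendix C:

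1. Add TEAE tables by SOC and PT, split into onset during treatment and onset after treatment to EOS. Onset during treatment runs from the first dose through the last dose plus a stated number of days, which the sponsor justifies from the drug's pharmacokinetics. Last dose plus 1 day, in SAP 8.4.3, is one existing convention, but it was written for selecting an ECG value.
2. Flag TEAEs that start during a dose interruption and show them in a separate row or sensitivity summary. Do not delete them from the by-dose tables, because removing them could understate events that follow soon after a poorly tolerated dose.

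AE onset dates and times (Protocol 12.2.5) and daily dosing records (Protocol 9.4) are already collected, so trial conduct does not change. The cost is a few extra tables and the need to choose and defend a boundary.
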